| 
• The spirometry test must be of good quality. If this is not the case, a re-test should be done. This re-test is covered by the current Informed Consent Form.• In compliance with ICH requirements, the protocol mentions that all results will be presented in an integrated report at the end of the study.• A description of how subjects will be included in the CMI sub-cohort and a description of how the sub-cohort will represent the fully randomized study groups has been added.• Following re-development and re-validation of the anti-PD ELISA, a new cut-off was defined.• Additional administrative changes have been performed:
– The IND number has been added.– The list of contributing authors as well as Sponsor signatory has been updated.– GSK Biologicals’ “Global Vaccines Clinical Laboratories (GVCL)” has been renamed as “Clinical Laboratory Sciences (CLS)”– Name “Quest Diagnostic Limited” has been replaced by “Q² Solutions” due to its merge with QLab.– Reference to the GSK Biologicals’ Laval laboratory was removed, as this laboratory will not be used in the study. In addition, this laboratory is no longer part of GSK Biologicals’ laboratories.– In addition, minor edits in other sections were made for clarification. | |

Protocol Amendment 2 Investigator Agreement

I agree:

- To conduct the study in compliance with this protocol, any future protocol amendments or protocol administrative changes, with the terms of the clinical trial agreement and with any other study conduct procedures and/or study conduct documents provided by GlaxoSmithKline (GSK) Biologicals.
- To assume responsibility for the proper conduct of the study at this site.
- That I am aware of, and will comply with, 'Good Clinical Practice' (GCP) and all applicable regulatory requirements.
- To ensure that all persons assisting me with the study are adequately informed about the GSK Biologicals' investigational vaccines and other study-related duties and functions as described in the protocol.
- To acquire the reference ranges for laboratory tests performed locally and, if required by local regulations, obtain the laboratory's current certification or Quality Assurance procedure manual.

3. Sponsor Study Monitor

Refer to the local study contact information document.

4. Sponsor Study Contact for Reporting of a Serious Adverse Event

GSK Biologicals Central Back-up Study Contact for Reporting SAEs: refer to protocol Section [8.4.2](#).

5. GSK Biologicals' Central Safety Physician On-Call Contact information for Emergency Unblinding

GSK Biologicals Central Safety Physician and Back-up Phone contact: refer to protocol Section [8.8](#).

SYNOPSIS

Detailed Title

A Phase I, randomised, observer-blind, placebo-controlled, multi-centre study to evaluate the safety, reactogenicity and immunogenicity of GSK Biologicals' GSK3277511A investigational vaccine when administered intramuscularly according to a 0, 2 months schedule in adults.

Indication

Immunisation against non-typeable *Haemophilus influenzae* (NTHi) and *Moraxella catarrhalis* (Mcat) in adults.

Rationale for the study and study design

- Rationale for the study**

GSK Biologicals is developing a new NTHi-Mcat investigational vaccine against diseases caused by NTHi and Mcat, such as respiratory tract infections in COPD (chronic obstructive pulmonary disease) patients, which can lead to acute exacerbations of COPD (AECOPD). The investigational vaccine that will be evaluated in the present study is a multi-component vaccine based on conserved surface proteins of NTHi and Mcat. Three NTHi proteins have been selected: Protein D (PD), as a free recombinant protein and Protein E (PE) and PilA protein, as a recombinant fusion protein named PE-PilA. The selected Mcat antigen is UspA2.

The purpose of this new Phase I study is to evaluate the safety, reactogenicity and immunogenicity of the NTHi-Mcat investigational vaccines, first in healthy young adults (18-40 years old) with a non-adjuvanted formulation and secondly in adults 50-70 years old having a significant smoking history (≥ 10 pack-years) with two adjuvanted formulations. The investigational vaccines will be administered according to a 0, 2 months schedule. Saline placebo will be used as control.

- Rationale for the study design**

As the UspA2 antigen has never been administered to human, healthy young adults will be enrolled and vaccinated with a non-adjuvanted vaccine in the study prior to vaccinate adults of 50-70 years old with the adjuvanted formulations. The study will hence follow a staggered design with two steps. Step 1 will include healthy adults 18-40 years old either receiving a non-adjuvanted (plain) vaccine containing 10 μ g of PD, 10 μ g of PE-PilA and 10 μ g of UspA2, or a placebo control. Step 2 will include adults 50-70 years old with a smoking history of at least 10 pack years either receiving placebo control, or one of two AS01_E-adjuvanted formulations, i.e. 10 μ g of PD, 10 μ g of PE-PilA and 10 μ g of UspA2 or 10 μ g of PD, 10 μ g of PE-PilA and 3.3 μ g of UspA2.

Moving to Step 2 or administration of vaccine Dose 2 within a step will be conditional on the favourable outcome of an evaluation of safety data obtained up to 7 days after administration of (a) previous vaccine dose(s) by an internal Safety Review Committee (iSRC).

- **Rationale for the use of placebo**

The placebo group (saline solution) is included in the NTHI MCAT-001 study as a control for both the safety and immunogenicity assessments.

Objectives

Primary

- To evaluate the safety and reactogenicity profile of the NTHi-Mcat investigational vaccines.

Secondary

- To evaluate the humoral and cellular immune response of the NTHi-Mcat investigational vaccines.

Tertiary

- To collect blood samples for assay development/validation and/or for evaluation/characterisation of the humoral and cellular immune responses to components of either the NTHi-Mcat investigational vaccines and/or of other respiratory pathogens.

Study design

- **Experimental design:** Phase I, observer-blind, randomised, placebo-controlled, multi-centric study with two steps.

- **Duration of the study:** For each subject, the study will last approximately 15 months, from screening to study end.

- Epoch 001: Primary starting at Screening Visit and ending at, and including Visit 6 (Day 90).
 - Epoch 002: Follow-up starting at Visit 7 (Day 210) and ending at Visit 8 (Day 420).

- **Study groups:**

- **10-10-10:** Approximately 15 subjects receiving two doses of the non-adjuvanted GSK Biologicals' NTHi-Mcat investigational vaccine containing 10 µg of PD, PE-PilA and UspA2 during Step 1 of the study.

- **PLACE1:** Approximately 15 subjects receiving two

doses of placebo (saline solution) during Step 1 of the study.

- **10-10-10-AS:** Approximately 30 subjects receiving two doses of the AS01_E-adjuvanted GSK Biologicals' NTHi-Mcat investigational vaccine containing 10 µg of PD, PE-PilA and UspA2 during Step 2 of the study.
- **10-10-3-AS:** Approximately 30 subjects receiving two doses of the AS01_E-adjuvanted GSK Biologicals' NTHi-Mcat investigational vaccine containing 10 µg of PD, 10 µg of PE-PilA, and 3.3 µg of UspA2 during Step 2 of the study.
- **PLACE2:** Approximately 30 subjects receiving two doses of placebo (saline solution) during Step 2 of the study.

Synopsis Table 1 Study groups and epochs foreseen in the study

| Study groups | Number of subjects | Age (Min/Max) | Epochs | | Step |
|--------------|--------------------|---------------|-----------|-----------|------|
| | | | Epoch 001 | Epoch 002 | |
| 10-10-10 | 15 | 18 - 40 years | x | x | 1 |
| PLACE1 | 15 | 18 - 40 years | x | x | 1 |
| 10-10-10-AS | 30 | 50 - 70 years | x | x | 2 |
| 10-10-3-AS | 30 | 50 - 70 years | x | x | 2 |
| PLACE2 | 30 | 50 - 70 years | x | x | 2 |

Synopsis Table 2 Study groups and treatment foreseen in the study

| Treatment name | Vaccine/ product name | Study Groups | | | | |
|----------------------------|-----------------------|--------------|-------------|------------|--------|--------|
| | | 10-10-10 | 10-10-10-AS | 10-10-3-AS | PLACE1 | PLACE2 |
| 10-10-10/Plain | NTHi-Mcat 10-10-10 | x | | | | |
| | NaCl | | | | | |
| 10-10-10/AS01 _E | NTHi-Mcat 10-10-10 | | x | | | |
| | AS01E | | | | | |
| 10-10-3/AS01 _E | NTHi-Mcat 30-30-10 * | | | x | | |
| | AS01E | | | | | |
| Placebo | NaCl | | | | x | x |

* Vials containing 37.5 µg, 37.5 µg and 12.5 µg of freeze-dried PD, PE-PilA and UspA2, respectively, will be diluted in three volumes of AS01_E (total of ~1875 µL). 0.5 mL will be administered.

- **Control:** placebo control (saline solution).
- **Vaccination schedule:** 0, 2 months (i.e. at Visit 1 [Day 0] and Visit 4 [Day 60]).
- **Treatment allocation:** Subjects will be allocated to a study group using a centralised randomisation system on internet (SBIR). SBIR will also be used for treatment allocation at second dose. The randomisation algorithm

will use a minimisation procedure accounting for centre at Step 1 and accounting for age (50-59 years or 60-70 years), for smoking status (current or former smokers), for centre and for forced expiratory volume in 1 second (FEV₁) / forced vital capacity (FVC) (≥ 0.7 or < 0.7) at Step 2.

- **Blinding:** Observer-blind.

Synopsis Table 3 Blinding of study epochs

| Study Epochs | Blinding |
|--------------|----------------|
| Epoch 001 | observer-blind |
| Epoch 002 | observer-blind |

- **Sampling schedule:**

- Blood samples for safety (haematology/ biochemistry) will be collected from all subjects at Screening Visit (pre-Day 0), at Visit 1 (Day 0), Visit 2 (Day 7), Visit 4 (Day 60), Visit 5 (Day 67), Visit 7 (Day 210) and at Visit 8 (Day 420).
- Blood samples for immunogenicity will be collected from all subjects for humoral immunity at Visit 1 (Day 0), Visit 3 (Day 30), Visit 4 (Day 60), Visit 6 (Day 90), Visit 7 (Day 210) and at Visit 8 (Day 420), and from a sub-cohort of subjects for cell-mediated immunity (CMI) at Visit 1 (Day 0), Visit 4 (Day 60), Visit 6 (Day 90), Visit 7 (Day 210) and at Visit 8 (Day 420).

- **Type of study:** self-contained
- **Data collection:** Electronic Case Report Form (eCRF)
- **Safety monitoring during vaccination period:** Safety evaluations by the Safety Review Team (SRT) and iSRC.

Moving to Step 2 or administration of vaccine Dose 2 within a step will depend on the favourable outcome of a safety evaluation based on the safety data collected up to 7 days after administration of the previous dose(s). In order to move to Step 2, safety data will be needed from all subjects. In order to move from Dose 1 to Dose 2 within a step, safety data from about 50% of the vaccinated subjects will be needed.

Number of subjects The target is to enrol ~30 eligible subjects 18–40 years old in Step 1 (~15/group) and ~90 eligible subjects 50–70 years old in Step 2 (~30/group). The total target number of subjects is ~120.

Endpoints**Primary**

- Occurrence of each solicited local and general adverse event (AE), during a 7-day follow-up period (i.e. day of vaccination and 6 subsequent days) post-Dose 1 and post-Dose 2, in all subjects, in all vaccine groups.
- Occurrence of any unsolicited AEs, during a 30-day follow-up period (i.e. day of vaccination and 29 subsequent days) post-Dose 1 and post-Dose 2, in all subjects, in all vaccine groups.
- Occurrence of haematological and biochemical laboratory abnormalities, after vaccination, in all subjects, in all vaccine groups:
 - Any haematological (RBC, WBC and differential count, platelets count and haemoglobin level) or biochemical (alanine aminotransferase [ALT], aspartate aminotransferase [AST] and creatinine) laboratory abnormality on Day 7, Day 60, Day 67, Day 210 and Day 420.
- Occurrence of any serious AE (SAE), occurring from first vaccination to study conclusion in all subjects, in all vaccine groups.
- Occurrence of any potential immune-mediated disease (pIMD) occurring from first vaccination to study conclusion in all subjects, in all vaccine groups.

Secondary

- Humoral immune response to the components of the NTHi-Mcat investigational vaccine formulations, on Day 0, Day 30, Day 60, Day 90, Day 210 and Day 420, in all subjects, in all vaccine groups:
 - Anti-PD, anti-PE, anti-PilA and anti-UspA2 antibody concentrations.
- Cell-mediated immune response to components of the NTHi-Mcat investigational vaccine formulations, on Day 0, Day 60, Day 90, Day 210 and Day 420, in a sub-cohort of subjects, in all vaccine groups:
 - Frequency of specific CD4⁺/CD8⁺ T-cells measured on cryopreserved peripheral blood mononuclear cells (PBMCs) and identified by flow cytometry intracellular cytokine staining (ICS) expressing two or more markers (such as IL-2, IL-13, IL-17, IFN- γ , TNF- α and CD40L).

TABLE OF CONTENTS

| | PAGE |
|--|------|
| SPONSOR INFORMATION | 7 |
| SYNOPSIS..... | 8 |
| LIST OF ABBREVIATIONS | 22 |
| GLOSSARY OF TERMS | 25 |
| 1. INTRODUCTION..... | 30 |
| 1.1. Background | 30 |
| 1.1.1. COPD: an introduction | 30 |
| 1.1.2. Current management of AECOPD | 30 |
| 1.1.3. GSK Biologicals' NTHi-Mcat investigational vaccine | 31 |
| 1.2. Rationale for the study and study design | 32 |
| 1.2.1. Rationale for the study | 32 |
| 1.2.2. Rationale for the study design..... | 33 |
| 1.2.3. Rationale for the use of placebo | 33 |
| 1.3. Benefit/Risk Assessment | 34 |
| 1.3.1. Risk Assessment | 34 |
| 1.3.2. Benefit Assessment..... | 34 |
| 1.3.3. Overall Benefit/Risk Conclusion..... | 34 |
| 2. OBJECTIVES..... | 35 |
| 2.1. Primary objective | 35 |
| 2.2. Secondary objective | 35 |
| 2.3. Tertiary objective | 35 |
| 3. STUDY DESIGN OVERVIEW | 36 |
| 3.1. Study design..... | 36 |
| 3.2. Safety precautions | 38 |
| 3.2.1. Details of the staggered design of the study | 38 |
| 3.2.2. Vaccination | 39 |
| 4. STUDY COHORT..... | 39 |
| 4.1. Number of subjects/centres | 39 |
| 4.2. Inclusion criteria for enrolment | 40 |
| 4.2.1. Healthy adults 18-40 years old (Step 1) | 40 |
| 4.2.2. Current and former smokers 50-70 years old (Step 2) | 41 |
| 4.3. Exclusion criteria for enrolment..... | 41 |
| 4.3.1. Healthy adults 18-40 years old (Step 1) | 41 |
| 4.3.2. Current or former smokers 50-70 years old (Step 2) | 43 |

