7.1.2. Analysis of safety

The primary analysis will be performed on the TVC and, if in any vaccine group and at any time point the percentage of vaccinated subjects excluded from the ATP cohort is at least 10%, a second analysis will be performed on the ATP cohort to complement the TVC.

The percentage of subjects with at least one local AE (solicited and unsolicited), with at least one general AE (solicited and unsolicited) and with any AE during the 7-day or 30-day follow-up period will be tabulated after Dose 1 and Dose 2 and overall with exact 95% CI. The same computations will be done for Grade 3 AEs, any AEs causally related to vaccination and any Grade 3 AEs causally related to vaccination.

The percentage of subjects/doses reporting each individual solicited local (any grade, Grade 3) and general (any grade, Grade 3, any causally related to vaccination and any Grade 3 causally related to vaccination) AE during the 7-days (Day 0 to Day 6) follow-up period will be tabulated for each group as follows:

- Overall, the percentage of subjects with the symptom and its exact 95% CI.
- Overall, the percentage of doses with the symptom and its exact 95% CI.
- At each study dose (visit), the percentage of subjects with the symptom and its exact 95% CI.

Statistical Analysis Plan

Study alias & e-track number(s): NTHI MCAT-001 (201281)

The exact 95% CIs will be calculated assuming independence between doses. For fever, additional analyses will be performed by 0.5°C increments.

The verbatim reports of **unsolicited symptoms** will be reviewed by a physician and the signs and symptoms will be coded according to the MedDRA Dictionary for Adverse Reaction Terminology. Every verbatim term will be matched with the appropriate preferred term (PT). The percentage of subjects with unsolicited symptoms within 30 days after any doses with its exact 95% CI will be tabulated by group and by MedDRA PT. Similar tabulation will be done for Grade 3 unsolicited symptoms, for unsolicited symptoms that resulted in a medically attended visit, for unsolicited symptoms causally related to vaccination and for Grade 3 symptoms causally related to the vaccination.

For each group and for each **haematology and biochemistry parameter**:

- The percentage of subjects having haematology and biochemistry results below or above the normal laboratory ranges will be tabulated by time point.

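### The unsolicited-AE primary endpoint is defined after Dose 1 and after Dose 2, but no summary table specified in the protocol or SAP isolates unsolicited AEs by dose

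*Protocol*

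**What the plan says.** The protocol (synopsis and section 10.1) and the current SAP (Amendment 2, section 5.1) define the endpoint in the same words: "Occurrence of any unsolicited AEs, during a 30-day follow-up period (i.e. day of vaccination and 29 subsequent days) post-Dose 1 and post-Dose 2".

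The analysis text is also the same in protocol 10.6.2, SAP 7.1.2 (Day 90 analysis) and SAP 7.2.2 (Day 420 analysis). It provides for three kinds of AE table:

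- **Unsolicited AEs alone, by group and preferred term.** "The percentage of subjects with unsolicited symptoms within 30 days after any doses with its exact 95% CI will be tabulated by group". The more specific versions follow the same format: "Similar tabulation will be done for Grade 3 unsolicited symptoms, for unsolicited symptoms that resulted in a medically attended visit", then related and Grade 3 related events. None is split by dose.
- **Overall AE tables, for each dose and overall.** These give the percentage of subjects with a local AE, "with at least one general AE (solicited and unsolicited) and with any AE during the 7-day or 30-day follow-up period". The same is done for Grade 3, related, and Grade 3 related AEs. Each row combines solicited and unsolicited events.
- **Individual solicited symptoms.** These are shown overall and by dose: "At each study dose (visit), the percentage of subjects with the symptom and its exact 95% CI".

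For unsolicited symptoms, SAP section 8 takes all vaccinated subjects as the denominator and counts non-reporters as event-free. SAP 9.1 mentions an assessment of unsolicited AEs after each dose but specifies no table for it, and provides individual listings only at the final analysis.

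**The concern.** The solicited endpoint uses the same post-Dose 1 and post-Dose 2 phrase and is tabulated by dose. Concomitant medication, which is not an endpoint, is also summarised by dose. Among these, only unsolicited AEs have their separate tables pooled.

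The design itself treats each dose as a separate safety question. UspA2 had not been given to humans before, and Dose 2 may start only after a favourable review of safety data following Dose 1 (protocol 1.2.2 and 8.10). Whether unsolicited events become more or less frequent after the second dose is something a reader of a two-dose Phase I report will ask. The planned summary tables do not answer it directly. The choice of formulation also depends on an acceptable safety profile (SAP 7.1.3.3), so the missing split bears on a decision that the trial is meant to support.

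**Working it through.** **The plan's own figures.** The point rests on no stated number, but the nearby ones reproduce. Protocol 10.3 gives about 78.5% for detecting an AE of 5% true incidence with 30 subjects: 1 − 0.95^30 = 0.7854. All 16 exact intervals in Table 23 (n = 15) also reproduce to one decimal.

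**Inputs.** The group size is 30 in Step 2 (protocol 10.3). The documents give no AE rates, so every rate below is an assumption. Let u1 and u2 be the unsolicited rates after Dose 1 and Dose 2, and s the rate of solicited events that count in the same row.

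**Step 1: the pooled table.** With events independent between doses, the either-dose rate is 1 − (1 − u1)(1 − u2).

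| u1 | u2 | Pooled rate |
|---|---|---|
| 10% | 30% | 1 − 0.90 × 0.70 = 37.0% |
| 30% | 10% | 1 − 0.70 × 0.90 = 37.0% |
| 20.65% | 20.65% | 1 − 0.7935² = 37.0% |

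A rise, a fall and no change give the same entry, about 11 of 30 subjects (exact 95% CI 19.9% to 56.1%).

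**Step 2: the combined per-dose rows.** With solicited and unsolicited AEs independent, the rate at a dose is 1 − (1 − u)(1 − s). If s is the same at both doses, the change between doses is (u2 − u1)(1 − s). For u1 = 10% and u2 = 30%:

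| Assumed s | After Dose 1 | After Dose 2 | Change shown |
|---|---|---|---|
| 30% | 37% | 51% | 14 points |
| 50% | 55% | 65% | 10 points |
| 70% | 73% | 79% | 6 points |
| 90% | 91% | 93% | 2 points |

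If the solicited rate also changes, from s1 to s2, the shift is (u2 − u1)(1 − s2) + (s2 − s1)(1 − u1). The two contributions cannot be separated from the combined row.

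**Step 3: the Grade 3 rows.** The relevant s is then the Grade 3 solicited rate. At an assumed 10%, a 20-point rise in Grade 3 unsolicited AEs would show as 20 × 0.90 = 18 points. The related rows gain less, because protocol 8.3.3.2.2 counts every solicited local reaction as related.

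**Step 4: what a separate table would show.** The same example reads 3/30 = 10% (exact 95% CI 2.1% to 26.5%) after Dose 1 and 9/30 = 30% (14.7% to 49.4%) after Dose 2. The 20 points appear undiluted, although the intervals are wide.

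**The case against.** The best counter-argument is that much of the information is already planned. The per-dose rows include Grade 3 and related versions, where dilution may be slight. Individual solicited symptoms are shown by dose, so a reader can set them against the combined rows. Listings follow at the final analysis. This stands as far as it goes, but the comparison only bounds an unsolicited change. It does not isolate one.

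A reader might infer that a between-dose change cannot be seen at all, or appears in no table. The documents do not support that, for the reasons just given. In addition, the SAP leaves table layouts to a TFL annex, which was not available. Nor should one quote only the severe case: solicited rates of 80%, 90% or 95% would shrink a 20-point rise to 4, 2 or 1 points, but those rates are assumed and apply to the row with the most masking.

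A reader might also infer that the SAP departs from the protocol. It does not, because protocol 10.6.2 pools in the same way. The endpoint phrase could be read as merely naming two collection windows. That reading is possible, but the per-dose handling of the identically worded solicited endpoint argues against it.

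Nor is second-dose safety unwatched. The internal committee reviews unblinded data up to the Day 7 visit after each dose, and holding rule 2c counts Grade 3 unsolicited events in the first seven days (protocol 8.10 and Table 22). Those reviews do not cover Days 7 to 29, and no individual study report is written from them.

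Finally, the pooled denominator mixes subjects who received one dose with those who received two. The documents give no discontinuation rate, so no effect can be sized, and all vaccinated subjects remains a normal base for an overall rate.

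**Conclusion.** The point holds for the specified summary tables: none reports unsolicited AEs separately by dose, although the endpoint names both doses. The pooled table cannot show a change or its direction. The combined per-dose rows retain a fraction (1 − s) of a change, which in the examples is 14, 10, 6 or 2 of 20 points. Those sizes rest on assumed rates, on independence and, for the combined rows, on an equal solicited rate at both doses.

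This is an endpoint-to-analysis mismatch shared by both documents. The safety analysis is descriptive, so no power or type I error is affected, and no data are lost. It is a cheap improvement that lets the trial report its own primary endpoint by dose.

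**What to change.** In SAP 7.1.2 and 7.2.2 and protocol 10.6.2, tabulate unsolicited AEs (any, Grade 3, medically attended, related, and Grade 3 related) from Day 0 to Day 29 after Dose 1, after Dose 2 and overall, each with an exact 95% CI. Use subjects who received the dose as the denominator of each per-dose column, and keep all vaccinated subjects for the overall column. Add the matching per-dose denominators to the table in SAP section 8.

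The cost is a wording change and two columns per table. Unsolicited AEs are already collected on separate diary cards after each vaccination (protocol 5.6.16), so no new data are needed. The small downside is longer preferred-term tables.
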